7.5 Recording of data and retention of documents

Data on patients collected on CRFs during the trial will be documented in an anonymous fashion and the patient will only be identified by the patient number, and by his/her initials if also required. If, as an exception, it is necessary for safety or regulatory reasons to identify the patient, both Medarex and the investigator are bound to keep this information confidential.

All the information required by the protocol must be provided and any omissions require explanation. All CRFs must be completed and available in a timely fashion, preferable no more than five (5) days after the patient's visit, so that the monitor may check the entries for completeness, accuracy and legibility, ensure the CRF is signed by the investigator and transmit the data to Medarex.

[figure not shown]
The investigator must maintain source documents for each patient in the study. All information on CRFs must be traceable to these source documents, which are generally maintained in the patient's file. The source documents must contain all demographic and medical information, including laboratory data, electrocardiograms, etc., as well as a copy of the signed informed consent form, which must indicate the study number and title of the trial.

[figure not shown]
The investigator must retain essential documents, listed below, as long as needed to comply with national and international regulations (generally two years after discontinuing clinical development or after the last marketing approval). Medarex will notify the investigator(s)/institution(s) when the study-related records are no longer required. The investigator agrees to adhere to the document retention procedures by signing the protocol. Essential documents include:

- IRB/IEC approvals for the study and all amendments to protocol
- All source documents and laboratory records
- CRF copies
- Patients' informed consent forms
- FDA form 1572
- Any other pertinent study document

7.6 Auditing procedures

In addition to the routine monitoring procedures, a Good Clinical Practice Quality Assurance audit may be conducted. This audit of clinical research activities is conducted to evaluate compliance with internal SOPs, and with the principles of Good Clinical Practice. A regulatory authority may also wish to conduct an inspection (during the study or even after its completion). If a regulatory authority requests an inspection, the investigator must inform Medarex immediately that this request has been made.

9.0 Administrative requirements

9.1 Publication of results

Any formal presentation or publication of data collected from this trial will be considered as a joint publication by the investigator(s) and the appropriate personnel of Medarex. Authorship will be determined by mutual agreement.

Medarex must receive copies of any intended communication in advance of publication (at least 15 working days for an abstract or oral presentation and 45 days for a journal submission). Medarex will review the communications for accuracy (thus avoiding potential discrepancies with submissions to health authorities), and to provide any relevant supplementary information. Authorship of communications arising from pooled data will include members of each of the contributing centers as well as Medarex personnel.

9.2 Administrative procedures

9.2.1 Changes to the protocol

Any change or addition to this protocol requires a written protocol amendment that must be approved by Medarex and the investigator before implementation. Amendments significantly affecting the safety of patients, the scope of the investigation or the scientific quality of the study, require additional approval by the IRB of all centers, and, in some countries, by the regulatory authority. A copy of the written approval of the IRB, which becomes part of the protocol, must be given to the Medarex monitor or their designee. Examples of amendments requiring such approval are:

- Increase in drug dosage or duration of exposure of patients
- Significant change in the study design (e.g. addition or deletion of a control group)
- Increase in the number of invasive procedures to which patients are exposed
- Addition or deletion of a test procedure for safety monitoring.

These requirements for approval must in no way prevent any immediate action from being taken by the investigator or by Medarex in the interests of preserving the safety of all patients included in the trial. If an immediate change to the protocol is felt to be necessary by the investigator and is implemented by him/her for safety reasons Medarex must be notified and the IRB at the center must be informed within 10 working days.

Amendments affecting only administrative aspects of the study do not require formal protocol amendments or IRB approval but the IRB of each center must be kept informed of such administrative changes. Examples of administrative changes not requiring formal protocol amendments and IRB approval that can be treated as administrative amendments include:

- Changes in the staff used to monitor trials (e.g. Medarex staff versus a CRO)
- Minor changes in the packaging or labeling of study drug.

9.2.2 Monitoring procedures

Before study initiation, at a site initiation visit or at an investigator's meeting, a Medarex representative will review the protocol and case report forms (CRFs) with the investigator(s) and their staff. During the study the Medarex monitor or their designee will visit the site regularly, to check the completeness of patient records, the accuracy of entries on the CRFs, the adherence to the protocol and to Good Clinical Practice, the progress of enrollment, and also to ensure that study medication is being stored, dispensed and accounted for according to specifications. The investigator and key trial personnel must be available to assist the Medarex monitor during these visits.

The investigator must give the monitor access to relevant hospital or clinical records, to confirm their consistency with the CRF entries. No information in these records about the identity of the patients will leave the study center. Medarex monitoring standards require full verification for the presence of informed consent, adherence to the inclusion/exclusion criteria, documentation of SAEs and the recording of primary safety variables. Additional checks of the consistency of the source data with the CRFs are performed according to the study-specific monitoring plan.

The investigator is responsible for completing the CRFs in a timely fashion, preferably within five (5) days of the patient's visit and the Medarex monitor is responsible for reviewing them and clarifying and resolving any data queries. A copy of the CRFs is retained by the investigator, who must ensure that it is stored with other study documents, such as the protocol, the investigators brochure and any protocol amendments, in a secure place.

The primary objective of this study is to assess the efficacy of ipilimumab. However, the study was terminated. So the efficacy data from this study will not be analyzed. This analysis plan will focus on analysis of subject safety information.

2. Study Description

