1.0 Introduction

1.1 Study Objective:

[figure not shown]
[figure not shown]
Primary Objective:

[figure not shown]
To assess the clinical response (PR and CR) to MDX-010 as a single agent in patients with locally advanced pancreatic adenocarcinoma.

To assess the clinical response (PR and CR) to MDX-010 as a single agent in patients with metastatic pancreatic adenocarcinoma.

Secondary Objective:

Define the MTD over the range of doses proposed.

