2.2.13 Biochemistry

In this study, patients will receive 3 mg/kg MDX-010 antibody intravenously every three weeks. Our experience with MDX-010 in patients with melanoma or renal cell cancer has shown a correlation between severe autoimmunity and tumor response. It has also shown a higher rate of both autoimmune toxicity and tumor response when MDX-010 is administered at repeated doses of 3 mg/kg. Two separate groups of 21-41 patients will be treated with intravenous infusion of MDX-010 at 3mg/kg for all doses. One of the groups will have locally advanced disease, while the other group will have distant metastases. The two groups will be evaluated separately using the same single arm, two-stage phase II design described in Section 5.5.

Four doses will be designated as a course of therapy and evaluations will be conducted at the end of each course, 3 weeks after the 4th infusion. An informal interim evaluation may be performed 3 weeks after the 2nd infusion to rule out rapid disease progression, but the formal evaluation with tumor measurements will be performed approximately 3 weeks after the 4th dose. CT scanning may be performed at any time during protocol implementation in the event that there is clinical evidence of disease progression

Treatment will be limited to 2 courses of therapy. Patients that respond and subsequently relapse will be treated with additional courses of therapy. Patients may come off study at any time if rapid disease progression occurs.

Patients in the locally advanced disease cohort may experience sufficient tumor response that their disease is rendered resectable. If this occurs, these patients will be treated with standard pancreatic resection rendering them NED (no evidence of disease).

3.2 Drug Administration:

MDX-010: All MDX-010 doses will be administered as an intravenous infusion controlled by an infusion pump. For administration, MDX-010 is to be injected into the IV bag and diluted in 0.9% Normal Saline, USP, to a concentration between 0.2 mg/ml and 1 mg/ml as specified in Section 8.1, and should be administered over 90 minutes through an add-on filter set with 1.2 µm air-eliminating filter [REDACTED]

Do not administer as an i.v. push or bolus. If \geq Grade 3 bronchospasm or other hypersensitivity reaction occurs, the infusion should be discontinued and no additional MDX-010 should be administered.

Surgical guidelines

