- Is \geq grade 3 severity infusion adverse event (occurring \leq 24 hours after start of infusion)

Events not considered to be serious adverse events are: hospitalizations occurring under the following circumstances--planned before entry into the clinical study, for elective treatment of a condition unrelated to the studied indication or its treatment, or part of the normal treatment or monitoring of the studied indication and not associated with any deterioration in condition; events occurring on an emergency, outpatient basis that do not result in admission (unless fulfilling the criteria above).

This study will utilize the CTC AE 3.0 for toxicity and adverse event reporting. A copy of the CTC AE 3.0 can be downloaded from the CTEP web site: <http://ctep.cancer.gov/reporting/ctc.html>. All appropriate treatment areas should have access to a copy of the CTC AE 3.0.

5.5 Statistical Section:

[figure not shown]
The primary objective of this study is to determine whether single agent MDX-010 antibody is able to result in clinical responses (PR or CR) in patients with stage IV pancreatic cancer. Our experience with MDX-010 in the melanoma and renal cell population has shown a correlation between autoimmune toxicity and tumor response.

For each of the two groups, this trial will be conducted as a Phase II clinical trial using an optimal design [REDACTED] The trial will seek

to rule out an undesirably low response probability of 5% ($p_0=0.05$) in favor of a level which demonstrates potentially useful activity of 20% ($p_1=0.20$). With an $\alpha=0.05$ (5% probability of accepting a poor combination, and $\beta=0.10$ (10% probability of rejecting a good combination), initially 21 patients will be enrolled. If 0-1 of 21 have a clinical response as defined in section 5.3, then accrual will stop and we will conclude that the combination is not sufficiently active in the disease being studied. If 2+/21 patients respond, then accrual will continue until 41 patients have been enrolled. If 2-4 of 41 respond, this will be insufficient activity to warrant further evaluation. If 5+/41 have documented clinical responses, the agent will be considered active in pancreatic carcinoma. Under this design if the null hypothesis were true (5% true response probability), there is a 72% probability of early termination.

It is expected that it will require 2-4 years to accrue up to 82 evaluable patients.

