2.1 Study Objectives

2.1.1 Primary Objective

The primary objective of this study is to assess the clinical response (partial response (PR) and complete response (CR)) to ipilimumab as a single agent in subjects with locally advanced pancreatic adenocarcinoma.

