5.8 Efficacy Analysis

Efficacy analysis will not be performed.

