5.10 Deviation from Protocol

The trial used the Simon two-stage optimal design [REDACTED] [REDACTED]. If at most one of 21 subjects enrolled in the first stage have a clinical response, then accrual will stop and we will conclude that the treatment is not sufficiently active in the disease being studied. If two or more of the 21 subjects respond, then accrual will continue until 41 subjects have been enrolled.

There was no clinical response in the first stage, so the trial was terminated.

The primary objective of this study is to assess the efficacy of ipilimumab. The planned efficacy analysis in protocol include: evaluation of target lesions and non-target lesions, evaluation of best overall response, duration of overall response and duration of stable disease. However, the study was terminated. So the efficacy data from this study will not be analyzed. The statistical analysis will be focused on subject safety information.

6. Data Imputation Rules

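### The SAP drops every summary of the primary endpoint because the trial stopped, although a stage 1 stop is a planned result of the design

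*SAP*

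**What the plan says.** **Protocol.** Section 1.1 sets two primary objectives, one per disease group. The second is "To assess the clinical response (PR and CR) to MDX-010 as a single agent in patients with metastatic pancreatic adenocarcinoma". The study design text before Section 3.2 adds: "The two groups will be evaluated separately using the same single arm, two-stage phase II design described in Section 5.5". Section 5.5 gives the first-stage rule: "If 0-1 of 21 have a clinical response as defined in section 5.3, then accrual will stop and we will conclude" that activity is insufficient. Section 5.3.1.3 defines best overall response, and 5.3.1.4 requires CR and PR to be confirmed.

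**SAP.** The opening statement reads: "However, the study was terminated. So the efficacy data from this study will not be analyzed". Section 5.8 says only: "Efficacy analysis will not be performed". Section 5.10 restates the 21/41 rule and reports: "There was no clinical response in the first stage, so the trial was terminated". It then lists the planned efficacy analyses, best overall response among them, drops them all, and ends: "The statistical analysis will be focused on subject safety information".

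The SAP's primary objective (2.1.1) covers response "to ipilimumab as a single agent in subjects with locally advanced pancreatic adenocarcinoma" and does not mention metastatic disease. Section 5.3 has the same limit, although 2.2.1 enrols both groups. The only analysis set in Section 3 is the safety population. In Appendix 1, Listings 4.1 to 4.4 keep lesion, response and survival data by subject. The table list passes from 3.1 to 5.1, and no title covers response.

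**The concern.** The SAP treats termination as if it had cut the trial off before its question could be answered. In a two-stage design a stop at 0 or 1 of 21 is one of the answers the design was built to give. It is the primary result.

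If the SAP is followed as written, neither primary objective gets a summary. A reader of the report learns that nobody responded in the first stage, but cannot tell:

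- whether that sentence covers one group or both;
- whether each group reached 21, so that the stopping rule was the reason accrual ended there;
- how many subjects had a tumor assessment after baseline;
- how the non-responders divide into stable disease, progression and not evaluable.

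The metastatic group is worst placed. It has no stated result of its own and no place in the SAP's objective.

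**Working it through.** **1. Inputs.** Protocol 5.5, repeated in SAP 5.3: p0 = 0.05, p1 = 0.20, alpha = 0.05, beta = 0.10; stage 1 n = 21, stop at 1 or fewer; total n = 41, active at 5 or more. Protocol 5.5 states a 72% probability of early termination under p0. Neither document gives the number enrolled or assessed by group.

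**2. The plan's own figure.** The stage 1 stop probability is P(X ≤ 1 | 21, p) = (1−p)^21 + 21·p·(1−p)^20.

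- p = 0.05: 0.3406 + 1.05 × 0.3585 = 0.717, which matches the stated 72%.
- p = 0.20: 0.0092 + 4.2 × 0.0115 = 0.058.

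The probability of declaring activity is the sum over x ≥ 2 of P(X1 = x | 21, p) × P(X2 ≥ 5−x | 20, p). It is 0.0457 at p0 and 0.902 at p1, so both error limits are met. A search for the smallest expected sample size under p0 also returns 1/21 and 4/41. The design is sound. For an inactive drug a stage 1 stop is the usual ending: 72% in each group, and 0.717² = 0.51 that both groups stop if they are independent.

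**3. What the design needs against what the SAP supplies.**

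| Needed for each group | Visible in the SAP |
|---|---|
| Number treated | Yes, by group (5.5 and 5.6; Tables 1.2 and 3.1) |
| Whether 21 was reached under the rule | Not stated; the 21 in 5.10 is the design number |
| Responders | Zero, in one sentence, group not named |
| Number assessed for response | Must be counted from listings |
| Best overall response | Listing 4.3 only, no table |

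**4. What the missing denominator does (illustration only).** The exact two-sided 95% upper limit for 0/n is 1 − 0.025^(1/n).

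| n assumed | Upper limit for 0/n |
|---|---|
| 21 | 16.1% |
| 18 | 18.5% |
| 16 | 20.6% |
| 10 | 30.8% |

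Across this range zero responders moves from incompatible to compatible with the 20% target. That is not the stopping criterion: 1/21 also stops, and its Clopper-Pearson interval is 0.1% to 23.8%. Protocol 5.5 plans a count rule and no interval, so the interval is an addition for reporting.

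**The case against.** The best defence is that the planned analysis was done. The protocol's primary analysis is a count rule. SAP 5.10 restates it, reports zero responses and draws the consequence. The paragraph just before that sentence speaks of 21 subjects in the first stage, so the denominator can be read as 21. If the sentence covers both groups, each result is zero over a number that Tables 1.2 and 3.1 will show. All data are listed, the omission is disclosed as a deviation, the stop stands, and hiding a zero cannot favour the drug. On that view this is a minor reporting gap.

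Much of this stands: the disclosure, the retained listings, the unchanged decision and the absence of any bias towards the drug. It is also true that parts of the SAP are not visible (Sections 4.2 and 5.7, for example), so the gap in table numbers proves little alone. The point rests on the explicit statements in the opening text, 5.8 and 5.10.

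The rest does not carry. The 21 in 5.10 belongs to the rule and is not an achieved count for either group. A single reference to the first stage does not say which of two separately evaluated groups it describes. Best overall response is not an objective, but 5.10 itself names it among the planned analyses. Leaving a reader to build the primary endpoint from listings, with confirmation applied by hand and no response population defined, is no substitute for a table.

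**Conclusion.** The concern holds. The SAP cancels the summary of its primary endpoint for a reason that the design itself treats as a result. Neither primary objective gets responders over n, and the metastatic objective is absent from SAP 2.1.1 and 5.3.

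The size is limited. If the zero in 5.10 covers the whole trial, the 0-to-1 responder condition is met in both groups and the conclusion of insufficient activity is unaffected. What is lost is the denominator, the group and the spread of best response. The upper limits of 16.1% to 30.8% rest on assumed numbers of 21 down to 10 per group and show only why the denominator matters. This should be fixed; it does not overturn the trial's decision.

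**What to change.** 1. Replace the text of SAP 5.8 with:

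> Confirmed objective response (CR+PR; Protocol 5.3.1, confirmation per 5.3.1.4) will be presented by group (locally advanced, metastatic) as responders / all treated subjects (safety population), with an exact (Clopper-Pearson) 95% CI. Treated subjects without a post-baseline tumor assessment count as non-responders. The same will be presented for response-evaluable subjects. Best overall response (CR, PR, SD, PD, not evaluable) will be tabulated by group.

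2. In the opening statement and in 5.10, replace the sentence that cancels the efficacy analysis with:

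> Efficacy analysis is limited to response rate and best overall response (Section 5.8).

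   Begin the safety-only sentence that follows in each place with *Apart from Section 5.8,*.

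3. In 5.10, give for each group the number enrolled, the number of responders and whether 21 was reached, so that it is clear whether accrual ended under the stage 1 rule or for another reason. Record which duration analyses (response, stable disease) are dropped.

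4. Add to Section 3:

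> Response-evaluable population: safety-population subjects with a baseline and at least one post-baseline tumor assessment, including unscheduled CT.

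5. List response and best overall response as parameters in Section 4, add the tables to Appendix 1 (no 4.x numbers appear in the table list), and name both groups in 2.1.1 and 5.3.

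The cost is SAP wording and one or two small tables from data already going into Listings 4.1 to 4.4. No patients or procedures are added. All treated subjects are the main denominator, so defining the evaluable set after the result is known cannot flatter it; that set serves to show how many were assessed.

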2.1 Study Objectives

2.1.1 Primary Objective

The primary objective of this study is to assess the clinical response (partial response (PR) and complete response (CR)) to ipilimumab as a single agent in subjects with locally advanced pancreatic adenocarcinoma.

2.2 Study Design

2.2.1 Overview

This is an open-label study of repeated doses of a human monoclonal antibody (mAb) to CTLA-4 (ipilimumab) administered to subjects with advanced pancreatic adenocarcinoma. It is designed to determine if a dose of ipilimumab at 3 mg/kg administered every 3 weeks can cause tumor regression. Subjects with measurable unresectable pancreatic carcinoma will be enrolled in two groups: locally advanced, unresectable disease group and metastatic disease group.

The study consists of three phases: Screening, Treatment, and Follow-up as shown in Table 1.

Table 1: Study Design

Phase	Screening	Treatment					Eval & follow-up
Visit	1	2	3	4	5	6 ³	variable ^{1,2}
Day(s)	-28 to 0	0	21 ±2d	Eval & 42 ±2d	63 ±2d	Eval & 84 ±2d	variable ¹
MDX-010		X	X	X	X	X	
1: 3-month intervals for 1 year, 6-month intervals for 2 years, and 12-month intervals until recurrence of disease. 2: Up to 2 subsequent courses of 4 infusions each ipilimumab (every 3 weeks x 4) may be given to subjects with complete or partial responses that have relapsed (PD). 3: A second course of 4 additional infusion ipilimumab (every 3 weeks x 4) may be given if the subject shows toxicities of grade 1 or less after the first course.							

Four doses will be designated as a course of therapy and evaluations will be conducted at the end of each course. An informal interim evaluation may be performed 3 weeks after the 2nd infusion to rule out rapid disease progression, but the formal evaluation with tumor measurements will be performed approximately 3 weeks after the 4th dose. CT scanning may be performed at any time during protocol implementation in the event that there is clinical evidence of disease progression. A second course of treatment may be offered to subjects with progressive disease who tolerate the first course of treatment and are willing to undergo a second course of treatment with ipilimumab rather than pursue an alternate therapy at that time.

Treatment will be limited to 2 courses of therapy. Subjects that respond (PR or CR) and subsequently relapse will be treated with up to 2 additional courses of therapy. Subjects may come off study at any time if rapid disease progression occurs.

Subjects in the locally advanced disease group may experience sufficient tumor response that their disease is rendered respectable. If this occurs, these subjects will be treated with standard pancreatic resection rendering them NED (no evidence of disease).

